Avapritinib is a selective and potent inhibitor of KIT and PDGFR $\alpha$ . Activating mutations in *KIT* and *PDGFRA* are the primary drivers of GIST in about 90% of patients (75-80% *KIT* and 10-15% *PDGFRA*). As described in [Section 1.2.1](#), avapritinib potently inhibits *KIT* and *PDGFRA* carrying the activating mutations most commonly found in GIST tumors. Avapritinib has demonstrated important clinical activity in an ongoing clinical study, BLU-285-1101, in patients with advanced, heavily pre-treated GIST. As described in [Section 1.2.3.1](#), the response rate with avapritinib was 16% among patients with *KIT*-driven GIST treated at doses of 300-400 mg QD. Importantly, these patients were heavily pre-treated, having received a median of 4 prior lines of therapy. The response rate was 71% among patients with *PDGFRA*-driven GIST across all dose levels. These patients had received a median of 1 prior line of therapy; however, *PDGFRA*-driven GIST is typically not responsive to any of the available TKIs, including imatinib. Based on preliminary data from this ongoing study the median PFS in patients with *KIT*-driven GIST was 11.5 months, and the median PFS in patients with *PDGFRA*-driven GIST was not yet reached.

Overall, avapritinib has been well-tolerated in patients with GIST. Most AEs have been Grade 1 or Grade 2 in severity and consistent with the effects of KIT inhibition. Adverse events occurring in  $\geq 25\%$  of patients (regardless of relationship to avapritinib) included nausea (56%), fatigue (53%), periorbital edema (43%), vomiting (41%), peripheral edema (34%), anemia (31%), diarrhea (31%), cognitive effects (consisting of multiple similar AEs aggregated into a single category [30%]), increased lacrimation (30%), and decreased appetite (28%). Among 116 patients treated with avapritinib in the BLU-285-1101 study as of the 11 October 2017 data cut-off only 6 (5%) have discontinued treatment due to a treatment-related AE.

Overall, the benefit-risk assessment is favorable and warrants continued development of avapritinib in patients with advanced GIST.

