### 5.3 Exclusion Criteria

Patients meeting any of the following criteria will not be eligible for participation in the study:

1. Patients who have received prior treatment with avapritinib or regorafenib.
2. Patients who have previously received more than 3 different TKIs for the treatment of GIST, including TKIs used for adjuvant therapy. Each different TKI is counted once

- regardless of how often it was used, and if 2 different TKIs are used in combination, both TKIs are counted.
3. Patients who are known to be both KIT and PDGFR $\alpha$  wild type.
  4. Patients who received any systemic anticancer therapy within 1 week before the first dose of study drug. Prior radiotherapy (including stereotactic radiotherapy) to major organs within 2 weeks of the first dose of study drug, or focal radiotherapy (including stereotactic radiotherapy), such as to bones, limbs, or other areas not involving major organs, within 3 days.
  5. Patients who have clinically significant, uncontrolled, cardiovascular disease, including congestive heart failure Grades II, III or IV according to the New York Heart Association classification, myocardial infarction or unstable angina within the previous 6 months, or uncontrolled hypertension.
  6. Patients who have experienced arterial thrombotic or embolic events such as cerebrovascular accident (including transient ischemic attacks) within 6 months before the first dose of study drug, or venous thrombotic events such as pulmonary embolism or deep vein thrombosis within 14 days before the first dose of study drug. Patients with venous thrombotic events such as pulmonary embolism or deep vein thrombosis  $\geq$  14 days before the first dose of study drug are not excluded provided they are on stable doses of anti-coagulation, or have completed the planned anti-coagulation regimen.
  7. Patients who have experienced any hemorrhage or bleeding event NCI CTCAE version 5.0 Grade 3 or higher within 4 weeks before the first dose of study drug.
  8. Patients who have a known risk of intracranial bleeding, such as a brain aneurysm that has not been removed or repaired, or a history of intracranial bleeding within 1 year prior to the first dose of study drug.
  9. Patients who have a symptomatic non-healing wound, ulcer, gastrointestinal perforation, or bone fracture.
  10. Patients who have poor organ function as defined by one or more of the following laboratory parameters:

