**Avapritinib**  
**Statistical Analysis Plan Study BLU-285-1303**

**1.1 Study Design**

This is an open-label, randomized, Phase 3 study in patients with locally advanced unresectable or metastatic GIST previously treated with imatinib and 1 or 2 other tyrosine kinase inhibitors (TKIs).

All study visits are intended to be conducted on an outpatient basis. After provision of written informed consent, patients will be evaluated for study eligibility during the screening period within 4 weeks (28 days) before study drug administration on Cycle 1 Day 1 (C1D1). During the screening period, eligibility will be confirmed; management of baseline concomitant conditions will be recorded and stabilized; baseline symptoms will be assessed; hematology, blood chemistry, mutation status, brain imaging (computed tomography (CT) scan or magnetic resonance imaging (MRI)), and baseline tumor assessments (CT scan or MRI) will be performed.

[figure not shown]
Approximately 460 patients are to be randomly assigned, in a 1:1 ratio, to 1 of 2 treatment arms: Arm A (avapritinib) or Arm B (regorafenib) stratified by TKI treatment (third versus fourth), geographic region (Asia versus rest of the world), and PDGFRA D842V mutation status measured in ctDNA or a tumor sample (PDGFRA D842V mutation present versus absent). PDGFRA D842V mutation present is defined if a PDGFRA D842V mutation is detected per local or/and central testing. At least 70% of the patients enrolled should be receiving the study drug as their third TKI treatment for GIST.

Patients randomized to Arm A will receive avapritinib 300 mg orally (PO) once daily (QD) with the option to escalate to 400 mg PO QD at the Investigator's discretion (the escalation option was removed in protocol amendment 3), if specific criteria are met as described in the protocol. Patients randomized to Arm B will receive regorafenib 160 mg PO QD for 3 weeks out of every 4 week (28 days) cycle (i.e., 3 weeks on/1 week off).

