**Avapritinib**  
**Statistical Analysis Plan Study BLU-285-1303**

**4.3.2 Baseline Disease Characteristics**

The number and percentage of patients in each of the following categories will be presented:

- Mutation Status
  - KIT V654A or T670I (Present, Absent)
  - KIT mutation status in KIT V654A and T670I mutation absent patients (Exon 17 mutation detected, KIT mutation other than exon 17 detected, no KIT mutation detected)
  - Specific Exon 17 mutations (D816X, D820X, N822X, Y823X) in KIT V654A and T670I mutation absent patients
  - PDGFRA D842V
  - PDGFRA non-D842V
- The Eastern Cooperative Oncology Group (ECOG) performance status (0, 1, 2)
- Metastatic disease (Yes, No)
- Largest target lesion size ( $\leq 5$  cm,  $>5$  to  $\leq 10$  cm,  $>10$  cm) by central radiology assessment
- Patient staged at screening by tumor/lymph nodes/metastasis (TNM) system (Yes, No)
- Current stage at screening by TNM
- Prior imatinib (Yes, No)
- Prior sunitinib (Yes, No)
- Primary tumor site of GIST at the time of diagnosis
- Site(s) of metastatic disease
- Prior surgical resection (Yes, No), and type of resection (total, partial, other).

Continuous baseline disease characteristics will be summarized using descriptive statistics.

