#### **4.6.5 Subgroup Analysis**

For ORR, DOR, and PFS as assessed by central radiology, and OS, the following subgroup analyses will be conducted. Corresponding forest plots will be provided based on the odds ratio or hazard ratio by treatment for each subgroup. Analyses will only be performed if the subgroup contains  $\geq 5$  patients.

- Age (<65 years,  $\geq 65$  years)
- Gender (Male, Female)
- Region (US, Europe, Asia, Other) \*Australia to be combined with Europe
- Race (White, Asian, Other)
- Largest target lesion ( $\leq 10$  cm,  $> 10$  cm)
- ECOG Performance Score at Baseline (0, 1)
- V654A or T670I Mutation Status (Present, Absent)
- PDGFRA D842V Mutation Status (Present, Absent)
- Stratification factors (Respective stratification levels).
- The following subgroup analyses will be performed in patients who are V654A mutation negative and T670I mutation negative:
  - D816X Mutation Status (Present, Absent)
  - D820X Mutation Status (Present, Absent)
  - N822X Mutation Status (Present, Absent)
  - Y823X Mutation Status (Present, Absent)

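### The Absent rows of the KIT-mutation subgroups in SAP 4.6.5 take in PDGFRA D842V tumours and pool patients with no KIT mutation detected, so they are not a clean KIT comparator

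*SAP*

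**What the plan says.** SAP 4.6.5 lists subgroup analyses, with forest plots of odds or hazard ratios, for ORR, DOR, PFS and OS. One row is "V654A or T670I Mutation Status (Present, Absent"). The rows for D816X, D820X, N822X and Y823X, also Present or Absent, carry a single restriction: "The following subgroup analyses will be performed in patients who are V654A mutation negative and T670I mutation negative". Neither set is limited to patients with a KIT mutation.

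D842V has its own row in the same list, "PDGFRA D842V Mutation Status (Present, Absent"), and a definition in SAP 1.1: "PDGFRA D842V mutation present is defined if a PDGFRA D842V mutation is detected per local or/and central testing". It is not used to filter the KIT rows.

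The baseline table in SAP 4.3.2 treats the same patients more finely. It divides those without V654A or T670I into exon 17 detected, "KIT mutation other than exon 17 detected, no KIT mutation detected", and tabulates PDGFRA D842V and non-D842V separately. So the SAP itself places patients with no detected KIT mutation among the V654A/T670I-absent.

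**The concern.** V654A, T670I and the four exon 17 codons are KIT mutations. Protocol 1.1.1 describes GIST as driven by a mutation in either KIT or PDGFRA, so a D842V tumour will ordinarily be Absent on all of these rows.

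D842V tumours are expected to behave differently. Protocol 1.4 reports: "The response rate was 71% among patients with *PDGFRA*-driven GIST across all dose levels". For KIT-driven GIST at 300-400 mg it gives 16%, and it says that PDGFRA-driven GIST typically does not respond to available TKIs.

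Two misreadings follow if Absent is taken as KIT-mutant disease without the named mutation. In the V654A/T670I row, D842V patients can make avapritinib look better without the mutation even if the mutation is irrelevant. In the exon 17 rows the same admixture raises the comparator and can mask an advantage in Present patients. Protocol 1.2.1 says the drug was designed for activation-loop mutants, so that contrast is a natural one to look for.

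**Working it through.** **The plan's own figures.** Protocol 10.2 and SAP 1.3 give 264 PFS events for 90% power at HR 0.67, two-sided 0.05. The Schoenfeld formula gives 4(1.960 + 1.282)² / (ln 0.67)² = 262.1, so 263 events; power at 264 is 90.2%. ORR 5% against 15% with 230 per arm gives 94.9% power against the stated 95% or so. These reproduce and are not in dispute. They supply the reference HR (0.67) and control ORR (5%) used below. The documents give no figures for the mutation subgroups.

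**Inputs from the documents.** Avapritinib ORR is 71% in PDGFRA-driven and 16% in KIT GIST at 300 mg or more (Protocol 1.2.3.1, 1.4). D842V is 5-10% of unresectable or metastatic disease (Protocol 1.1.2). SAP 3.1 provides for fewer than 24 D842V patients, and 24/460 = 5.2%, so 2% is also examined.

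**Assumptions.** V654A/T670I is present in 15-45% of patients. D842V patients have no co-detected KIT mutation. V654A/T670I has no effect of its own. Control ORR in D842V is 5% or 0%.

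**Response.** With d the D842V share of all patients and v the V654A/T670I share, the D842V share of the Absent row is w = d/(1 − v). Avapritinib ORR in the row is 0.16 + 0.55w. Without D842V, the odds ratio is (0.16/0.84)/(0.05/0.95) = 3.62.

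| d | v | w | Avapritinib ORR | OR, control 5% throughout | OR, control 0% in D842V |
|---|---|---|---|---|---|
| 2% | 15% | 2.4% | 17.3% | 3.97 | 4.07 |
| 2% | 30% | 2.9% | 17.6% | 4.05 | 4.18 |
| 2% | 45% | 3.6% | 18.0% | 4.17 | 4.34 |
| 5% | 15% | 5.9% | 19.2% | 4.53 | 4.82 |
| 5% | 30% | 7.1% | 19.9% | 4.73 | 5.11 |
| 5% | 45% | 9.1% | 21.0% | 5.05 | 5.58 |
| 10% | 15% | 11.8% | 22.5% | 5.51 | 6.28 |
| 10% | 30% | 14.3% | 23.9% | 5.95 | 7.00 |
| 10% | 45% | 18.2% | 26.0% | 6.68 | 8.24 |

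An exon 17 Absent row also loses the patients with that codon mutated, so its D842V share is at least as large as w.

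**PFS.** The model is exponential PFS with control median 5 months, 18 months of uniform accrual (a simplification of the plan's accrual pattern) and 6 months of follow-up. The HR is 0.67 in KIT patients and an assumed 0.2 or 0.4 in D842V. The pooled Cox HR of the Absent row, from 300,000 simulated patients, is:

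| D842V share of the row | D842V HR 0.2 | D842V HR 0.4 |
|---|---|---|
| 2% | 0.656 | 0.663 |
| 5% | 0.634 | 0.658 |
| 10% | 0.600 | 0.635 |
| 15% | 0.571 | 0.622 |

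Solving the same model numerically, without simulation, agrees to within 0.005 in every cell.

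**No KIT mutation detected.** If this group alone is 10-30% of the row (assumption), the pooled HR is 0.65 to 0.61 when its own HR is 0.5, unchanged when 0.67, and 0.69 to 0.75 when 1.0. With D842V at 5% of the row (HR 0.2) and undetected patients at 20%, the pooled HR is 0.64, 0.69 or 0.72 for an undetected HR of 0.67, 1.0 or 1.3. The net shift can take either sign.

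**The case against.** The SAP never labels Absent as KIT-mutant GIST. As a description of all trial patients without the named mutation, the row is computed correctly. That stands: the bias arises only when the row is read as the KIT comparator, which a row defined by a KIT mutation invites.

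The inputs are soft. The 5-10% is a background figure, not this trial's expected share, and at 2% the HR moves by only 0.01-0.02. The 71% and 16% are not like for like: D842V patients had a median of 1 prior regimen and all dose levels are included, while KIT patients had a median of 4 and the 16% is for 300 mg or more. Protocol 1.2.3.1 also counts 21 responses in 31 D842V patients, which is 67.7%, not 71%. Using 67.7% with 5% control and v = 15-30%, the odds ratio at 5-10% D842V is 4.5-5.8, so little changes. These points limit the size, not the direction for D842V.

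Much is reported elsewhere: D842V has its own row, SAP 4.6.2 plans PFS curves by stratification factor, and Protocol 10.5.6 plans correlation of baseline mutation status with outcome. The exploratory section, SAP 4.6.4, is redacted and may hold more. SAP 7.3 adds an Unknown or Missing category where information is unavailable, but does not say that this covers a test that found nothing. None of the visible text removes D842V from the KIT rows.

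A reader might infer that both groups inflate the Absent rows. The documents give no outcome data for patients with no KIT mutation detected, so no direction can be claimed for them. Nor do they show that most such patients had uninformative samples: the exclusion in Protocol 5.3 ("Patients who are known to be both KIT and PDGFR"α wild type) covers only known double wild types, so undetected ones may enrol.

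**Conclusion.** The point holds for D842V. Followed as written, SAP 4.6.5 puts these patients in every KIT Absent row unless a KIT mutation is co-detected, and moves each row towards avapritinib as a KIT comparator. If V654A/T670I has no effect, the Absent odds ratio goes from 3.6 to about 4.0-4.3 at 2% D842V. At 5-10% it is about 4.5-6.0, with V654A/T670I in 15-30% and 5% control response throughout; the widest assumptions reach 8.2. The PFS HR moves by about 0.01-0.02 when D842V is 2% of the row, and to about 0.57-0.66 at 5-15%, for an assumed D842V HR of 0.2-0.4. The actual share is unknown, so the effect may be small.

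For patients with no KIT mutation detected, the defect is pooling a group of unknown direction that the SAP already identifies. It would be wrong to conclude that the Absent rows overstate benefit overall. It would also be wrong to see a threat to the trial's main result: these subgroups lie outside the PFS, ORR, OS sequence in SAP 4.6.1.

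**What to change.** In SAP 4.6.5, run the V654A/T670I row and the four exon 17 rows in PDGFRA D842V-absent patients, and show no KIT mutation detected as its own level instead of pooling it into Absent. D842V patients remain visible in their existing row. SAP 4.3.2 already derives the categories. The text should also say whether a failed or missing sample counts as Unknown and a completed test that finds nothing as no KIT mutation detected.

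The cost is SAP wording and a subgroup filter, with no new data. The Absent rows become smaller, and patients with a KIT mutation detected are selected on detectability, which a footnote should state. Each single-codon Absent row will still contain patients with other exon 17 mutations; this change does not address that.

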#### **4.7 Safety Analyses**

Safety will be evaluated by the incidence of AEs, causality, intensity, seriousness, and outcome of AEs, the patient's vital signs, ECOG PS, clinical laboratory test results, and ECG data.

All safety data will be summarized by treatment group for the Safety Population.

#### **4.7.1 Adverse Events**

Adverse Events will be analyzed using treatment-emergent adverse events (TEAEs). The TEAE definition is dependent on the study period (e.g., main study treatment period) reported. An AE is considered a TEAE for a specified study period if the AE occurs during or after administration of the first dose of study drug from the same study period through up to the earlier of the last dose of study drug in that period + 30 days or the day before the start of crossover/extended treatment.

Adverse Event refers to TEAEs unless otherwise specified throughout this document. All AEs will be coded using MedDRA version 18.1. The severity will be graded using the National Cancer Institute (NCI) Common Terminology Criteria for Adverse Events (CTCAE), version 4.03 (patients enrolled before protocol amendment 2) and 5.0.

A patient experiencing multiple AEs under the same PT or SOC will be counted only once for that PT or SOC by maximum severity. If a patient experiences the same AE more than once with more than one causal relationship to study drug, the strongest causal relationship to study drug will be given precedence. Any missing severity, causality, or outcome will not be imputed and classified as 'Missing'. Detailed imputation rules for missing AE dates are in [Section 7.1](#).

The number of patients with at least one AE will be summarized ([Table 4](#)). The following tables summarize incidences of various aspects of AEs and serious adverse events (SAEs):

1. AE Summary (including all subsequent items)
2. AE by PT
3. AE by SOC and PT
4. AE related to study drug by PT
5. AE related to study drug by SOC and PT
6. SAE by PT
7. SAE by SOC and PT
8. SAE related to study drug by PT
9. SAE related to study drug by SOC and PT
10. Grade 3/4/5 AE by PT
11. Grade 3/4/5 AE by SOC and PT
12. Grade 3/4/5 AE related to study drug by PT
13. Grade 3/4/5 AE related to study drug by SOC and PT
14. AE by PT and NCI CTCAE Grade
15. AE by SOC, PT, and NCI CTCAE Grade

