### 2.2 Secondary Objectives

The key secondary objectives are:

- To evaluate ORR determined by central radiology assessment per mRECIST, version 1.1 in patients with advanced GIST treated with avapritinib compared to patients treated with regorafenib.

- To evaluate overall survival (OS) in patients with advanced GIST treated with avapritinib compared to patients treated with regorafenib.

To preserve study-wide Type I error, the key secondary objectives will be tested in the order presented, as part of the sequential testing scheme for the study if the primary analysis is significant.

Additional secondary objectives are:

- To evaluate the European Organisation for Research and Treatment of Cancer Quality of Life (EORTC-QLQ-C30) individual scores in patients with advanced GIST treated with avapritinib compared to patients treated with regorafenib.
- To evaluate the safety and tolerability of avapritinib compared to regorafenib.
- To evaluate disease response rate as assessed by the Investigator per mRECIST, version 1.1 and determined by central radiological assessment per Choi criteria in patients with advanced GIST treated with avapritinib compared to patients treated with regorafenib.
- To evaluate DCR per mRECIST, version 1.1 in patients with advanced GIST treated with avapritinib compared to patients treated with regorafenib.
- To evaluate duration of response (DOR) per mRECIST, version 1.1 in patients with advanced GIST treated with avapritinib compared to patients treated with regorafenib.
- To determine steady state systemic exposure of avapritinib.
- To assess the patient-reported perception of abdominal pain.

■ [REDACTED]

■ [REDACTED]

■ [REDACTED]

■ [REDACTED]

■ [REDACTED]

■ [REDACTED]

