**1.2.3 Exploratory Objectives**

### **1.3 Sample Size Justification**

The sample size calculation was based upon the assumption that the median PFS for regorafenib is approximately 5 months (Demetri 2013). Assuming avapritinib can reduce the risk of PFS events by 33%, i.e., a hazard ratio (HR) of 0.67 (avapritinib compared to regorafenib), a minimum of 264 PFS events are needed to provide 90% power at a 2-sided alpha of 0.05 for the study. With an 18-month accrual period and a 6-month follow-up period, the total sample size needed for the study is approximately 460 patients (230 patients per arm). This sample size takes a 2% dropout rate into consideration and assumes accrual will follow a truncated exponential distribution with a scaled power parameter of -9.

The sample size calculated for the primary endpoint, PFS, is also sufficient to detect a difference in ORR between the two arms. Assuming a null ORR of 5% and an alternative ORR of 15%, a sample size of 460 patients provides approximately 95% power to detect a difference in ORR using a test of two-proportions at a 2-sided alpha of 0.05.

Assuming the same effect size for OS as PFS (HR = 0.67), the same number of events (264) is required to power the OS analysis. The timing of the OS analysis will occur later than the PFS analysis as it will be at such time when 264 deaths occur.

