#### **4.7.2 Adverse Events of Special Interest**

Adverse events of special interest (AESI) will be summarized by category (cognitive effects and intracranial bleeding) and relevant PTs.

- Cognitive effects consisting of 4 PTs: cognitive disorder, memory impairment, confusional state, encephalopathy
- Intracranial bleeding consisting of 3 PTs: haemorrhage intracranial, cerebral haemorrhage, subdural haematoma.

The general rules for summarizing AE specified in [Section 4.7.1](#) apply for AESIs for avapritinib. The following AESI tables will be presented:

- AESI by AESI category and PT
- AESI related to study drug by AESI category and PT
- Serious AESI by AESI category and PT
- Serious AESI related to study drug by AESI category and PT
- Grade 3/4/5 AESI by AESI category and PT

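### Adverse events are compared only as crude percentages although the design assumes longer treatment on avapritinib; under equal monthly risks this adds about 0.6 to 4 points to the avapritinib arm at the planned cutoff, and patient-time rates should be added.

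*SAP*

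**What the plan says.** Protocol 2.2 lists as a secondary objective "To evaluate the safety and tolerability of avapritinib compared to regorafenib". SAP 4.7.1 carries this out by counting: "The number of patients with at least one AE will be summarized", followed by 29 tables by preferred term, system organ class, grade, seriousness, relatedness and action taken. SAP 4.7.2 extends the approach to cognitive effects and intracranial bleeding ("The general rules for summarizing AE specified in" Section 4.7.1 apply), and SAP 4.7.3 does so for dementia terms. Under SAP 7.3, percentages are normally taken over patients assessed. Protocol 10.5.4.1 also specifies incidences only.

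The counting window in SAP 4.7.1 starts at first dose. It closes 30 days after the last dose of that period or, if earlier, on the day before crossover or extended treatment. Under Protocol 4.1, treatment may continue until progression, toxicity or another listed reason. The SAP introduction says the analyses use data up to the cutoff of the 264-event PFS analysis.

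SAP 4.5 tabulates treatment duration and dose intensity separately, overall and per 4-week period. Neither document plans an event rate per unit of patient-time, a time-to-first-event analysis or a fixed-window comparison of adverse events.

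**The concern.** A crude percentage answers how many patients had the event while they were being observed. If one arm is observed longer, it collects more events at the same monthly risk. Here the trial's own hypothesis makes the arms unequal: if avapritinib delays progression as planned, its patients stay on drug longer and their window is longer. An excess of some points on avapritinib could then be read as toxicity when it reflects only benefit. If avapritinib exposure turned out shorter, the same tables would make the drug look safer than it is. At stake is how the Grade 3 or higher, serious and special-interest events are read in the benefit-risk assessment. No efficacy conclusion is affected.

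**Working it through.** **Inputs, all from SAP 1.3 unless noted.** "the median PFS for regorafenib is approximately 5 months"; HR 0.67; "a minimum of 264 PFS events are needed to provide 90% power at a 2-sided alpha of 0.05"; "With an 18-month accrual period and a 6-month follow-up period"; the plan "assumes accrual will follow a truncated exponential distribution with a scaled power parameter of -9"; 2% dropout; 460 patients, 1:1. The 30-day window is from SAP 4.7.1.

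**The plan's own figure first.** The Schoenfeld formula gives 4 × (1.960 + 1.282)² / (ln 0.67)² = 42.03 / 0.1604 = 262.1, so 263 events; 264 events give 90.2% power. Let λ be the PFS hazard: ln 2 / 5 = 0.1386 per month for regorafenib and 0.67 × 0.1386 = 0.0929 for avapritinib (median 7.46 months). With the SAP's accrual shape, time from entry to cutoff is C = 6 + X, where X is exponential with rate 9/18 = 0.5 truncated to 0–18 months (mean C about 8.0 months). Hence E[exp(−sC)] = exp(−6s) × 0.5/(0.5 + s) × (1 − exp(−18(0.5 + s)))/(1 − exp(−9)). Expected events are 230 × (0.659 + 0.517) = 270.5, and × 0.98 for dropout = 265. The design reproduces, with entry concentrated late. Uniform accrual would give 352 events by month 24, so it is only a sensitivity case.

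**Time at risk.** Taking exposure as time to PFS event, mean exposure is (1 − E[exp(−λC)])/λ. At the planned cutoff this is 0.659/0.1386 = 4.8 months on regorafenib and 0.517/0.0929 = 5.6 on avapritinib. With complete follow-up it is 1/λ: 7.2 and 10.8 months.

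**Chance of at least one event.** Let h be the same constant monthly hazard in both arms.

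- Without the window: P = h/(h + λ) × (1 − E[exp(−(h + λ)C)]). With complete follow-up this becomes h/(h + λ).
- With a window of w = 30/30.4375 = 0.986 months: P = 1 − exp(−hw) × [λ/(h + λ) + h/(h + λ) × exp((h + λ)w) × E[exp(−(h + λ)C)]].

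Example at h = 0.05, planned cutoff, no window. Regorafenib: 0.05/0.1886 × (1 − 0.234) = 20.3%. Avapritinib: 0.05/0.1429 × (1 − 0.330) = 23.4%.

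Regorafenib vs avapritinib, % (excess in points, from unrounded values):

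| Scenario | h = 0.01 | h = 0.05 | h = 0.10 | Largest at any h |
|---|---|---|---|---|
| Planned cutoff, SAP accrual, 30-day window | 5.2 vs 5.8 (0.6) | 22.9 vs 25.5 (2.5) | 39.6 vs 43.5 (3.9) | about 4.7 |
| Same, no window | 4.6 vs 5.4 (0.8) | 20.3 vs 23.4 (3.1) | 35.1 vs 40.1 (5.0) | about 6.6 |
| 24 months, uniform accrual, window | 6.5 vs 8.0 (1.5) | 27.3 vs 32.3 (5.0) | 44.7 vs 51.4 (6.7) | 6.9 |
| Complete follow-up, no window | 6.7 vs 9.7 (3.0) | 26.5 vs 35.0 (8.5) | 41.9 vs 51.8 (9.9) | 10.0 |

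The last maximum has a closed form: (1 − √0.67)/(1 + √0.67) = 0.0998, reached at h = 0.1135.

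**By event frequency.** For regorafenib percentages of 5, 50 and 95, the excess is 0.6, 4.4 and 1.5 points in the first row, and 2.3, 9.9 and 1.6 in the last. Events at or below 5%, or at or above 95%, stay under 3 points in every scenario.

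**Same data per patient-time.** At h = 0.05, planned cutoff, no window, mean time to first event or end of exposure is (1 − 0.234)/0.1886 = 4.06 months on regorafenib and (1 − 0.330)/0.1429 = 4.69 on avapritinib. The rates are 0.203/4.06 and 0.234/4.69, both 5.0 per 100 patient-months. The artefact disappears.

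**The case against.** The adverse event tables are descriptive and no between-arm test is planned. The avapritinib and regorafenib columns are limited to the main treatment period (SAP 3.2.7), so continuation after progression does not inflate that comparison. Exposure is tabulated, every event is listed by patient, and Protocol 10.5.4.3 allows further safety analyses. All of this is true. It lets a reader see that exposure differs, but not how much of a difference in percentages comes from it, and a general permission prespecifies nothing. SAP 3.2.7 also adds an overall avapritinib column that pools both periods, so the mismatch with the main-period regorafenib column is larger still.

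The objection to the size also stands. Treatment ends for reasons other than progression, and the documents state neither an expected treatment duration nor an event hazard. Extra discontinuation at 0.05 per month in both arms lowers the complete-follow-up maximum from 10 to about 7 points. Early-onset events would show less; a larger true difference in exposure would show more.

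Three stronger readings are tempting and not supported. First, a reader might take 10 points as the expected distortion, but that needs complete follow-up and the safety tables stop at the PFS cutoff. Second, a reader might suppose the problem is worst for cognitive effects and intracranial bleeding because they start late. Neither document gives their time to onset, the calculation assumes a constant hazard, and for uncommon events the artefact is smallest. Third, a reader might infer that a failed trial would hide harm. That holds only if avapritinib exposure is actually shorter; an HR near 1 gives equal exposure under this model.

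**Conclusion.** The point holds as a free improvement, not as an error that invalidates a planned analysis. The safety comparison has no adjustment for time at risk, and the design's own assumptions tilt it against avapritinib. For hazards of 0.01 to 0.10 per month the tilt is about 0.6 to 4 points at the planned cutoff with the SAP's accrual shape and 30-day window, and 0.8 to 5 without the window. It reaches about 7 under uniform accrual with the window, and 10 only with complete follow-up. These sizes rest on three assumptions that the documents do not fix: exposure equal to time to PFS event, exponential times, and a constant event hazard equal in both arms. The direction needs only longer exposure on avapritinib.

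**What to change.** In SAP 4.7.1 and 4.7.2, keep the crude tables and add exposure-adjusted incidence for the main treatment period: patients with a first event per 100 patient-months, with time at risk running to the first event or the end of the treatment-emergent window. Give the rate difference or ratio with 95% CI between arms. Do this for all adverse events, Grade 3 or higher, serious events, events leading to discontinuation, and each special-interest category.

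For cognitive effects and intracranial bleeding, add a time-to-first-event display (Kaplan-Meier or cumulative hazard) censored at the end of the window. State that the rate assumes a roughly constant hazard and that this censoring may be informative. Cumulative incidence curves with treatment end as a competing event would not serve. Under equal hazards they level off at h/(h + λ), which is 26.5% vs 35.0% at 0.05 per month and so reproduces the artefact. They would also drop events in the 30 days after the last dose.

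The cost is a few tables and two figures. Dose dates are already used for treatment duration (SAP 4.5.1) and onset dates are recorded (Protocol 9.8). Trial conduct, alpha and sample size do not change. The additions should be specified before database lock.
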